### **Study Procedures**

Study procedures are illustrated in figure, below. The estimate of the number of participants reflects the expectation of attrition due to the length of the study. Potential participants will be screened online and over the telephone for inclusions and exclusions as outlined above. Informed consent, pretest, posttest, and follow-up testing sessions will be completed online. The online cognitive training protocols are largely completed online from the participants' home or other location of their choosing. All protocols include interactive components; in some cases this involves telephone calls and/or online discussion with research personnel. Total participation duration is 17 weeks. Data collection is planned to be completed within one year of REB approval.

Interested participants who replied by email to the study advertisement (see Appendix) will be emailed the information sheet portion (excluding the signature section) of the informed consent, and will be asked to complete the online screening form and phone screening interview (see script in Appendix). Eligible participants will then be emailed a link to an online pre-test assessment. As the bulk of the study will be taking place online, participants will accept provisions of the study through an online consent form.

Following completion of the pre-test assessment session, participants will be randomly assigned to one of four groups according to a blocked randomization scheme (stratified on age, gender, and education) created by a study team member unknown to participants or otherwise involved in data collection procedures. Participants will be informed of their group allocation by email and then begin the assigned program at their convenience, immediately following the completion of the pretest.

The intervention groups are as follows:

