### **Statistical analyses**

Mixed-model ANOVAs will be used to examine pre-test and post-test scores on the outcome measures in the control and intervention groups. We will compare pre-test to immediate post-test and pre-test to follow-up post-test. The multiple test periods will be within-group repeated measures, and group assignment will be a between-groups variable. We expect significant interactions between group and pretest-posttest scores, with greater improvements over repeated test periods in the intervention group than the control.

This analysis will be done for each of the primary outcomes for both interventions. The same tests will be run on secondary outcomes to contrast the relevant intervention-control pair (e.g., GMT secondary outcomes measured/tested for GMT and BrainHQ, MAP secondary outcomes measures/tested in MAP and test-retest (waitlist) group.

No adjustments will be used for these primary and secondary *a priori* analyses.

We will also explore whether key variables including age, degree of engagement with the program, presence of subjective cognitive impairment, and computer familiarity covary with the effects of the intervention, and if so control for them by adding them as covariates in our statistical models.

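### The group-by-time test on the six primary measures is a change-score test that does not adjust for the pre-test: valid, but usually less precise than it could be

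*Combined protocol and SAP*

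**What the plan says.** The Statistical analyses section plans mixed-model ANOVAs: "The multiple test periods will be within-group repeated measures, and group assignment will be a between-groups variable". The contrasts are pairwise in time: "We will compare pre-test to immediate post-test and pre-test to follow-up post-test". The effect of interest is the interaction: "We expect significant interactions between group and pretest-posttest scores, with greater improvements over repeated test periods in the intervention group than the control". On scope: "This analysis will be done for each of the primary outcomes for both interventions". The Primary Outcome Measures section lists six instruments.

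The pre-test score is nowhere named as a covariate, and no model with a common pre-test mean across groups is described. One sentence rules out adjustments in the a priori analyses without saying whether it means covariates or multiplicity. The last paragraph allows exploratory, conditional covariates from an open list that names age, engagement, subjective impairment and computer familiarity.

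On timing, Study Procedures states: "Following completion of the pre-test assessment session, participants will be randomly assigned to one of four groups". The randomisation is blocked and stratified on age, gender and education. The Study population section gives 200 participants. The allocation ratio is not stated, and dropout is expected without a rate: "The estimate of the number of participants reflects the expectation of attrition due to the length of the study".

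**The concern.** With two time points, the group-by-time interaction compares mean change between groups. It subtracts the whole pre-test score from the post-test score, whatever the correlation between them. When the regression slope of post-test on pre-test is below 1, this over-corrects and adds noise. Adjusting for the pre-test estimates the slope from the data and removes that noise.

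This matters because the contrasts are small. If allocation is equal, 200 / 4 = 50 per arm before dropout. The documents give no power calculation, so nothing shows that the design can afford lost precision. For the primary measures, the score that would recover it is already collected before allocation. No conclusion becomes invalid; the usual cost is a wider confidence interval and lower power.

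**Working it through.** **The plan's own figure.** The only design figure is the total of 200. It cannot be reproduced, because the documents give no significance level, power, effect size, SD, pre-post correlation or dropout rate.

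**Inputs.** From the documents: the two-period contrasts, the group-by-time test, a pre-test before randomisation, 200 participants and four groups. Assumed: rho from 0.5 to 0.8; k = 0.8, 1 or 1.25; 40 completers per arm; a two-arm contrast; two-sided 5% level; 80% power.

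**Step 1: equivalence.** In one simulated data set with 50 per group, the interaction F was 4.3424 and the squared t for the difference in change scores was also 4.3424.

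**Step 2: variances.** Set the pre-test SD to 1 and the post-test SD to k.

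- Change score: 1 + k² − 2·rho·k
- Adjusted for pre-test: k²(1 − rho²)
- Share saved: (1 − rho·k)² / (1 + k² − 2·rho·k)

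At k = 1 the share saved is (1 − rho)/2. It is zero only when rho·k = 1. Example at rho 0.6, k = 1: the change variance is 1 + 1 − 1.2 = 0.80, the adjusted variance is 1 − 0.36 = 0.64, and the saving is 1 − 0.64/0.80 = 20%.

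**Step 3: detectable effect and power.** These come from the noncentral t with n = 40 per arm. The degrees of freedom are 2n − 2 = 78 for the planned test and 2n − 3 = 77 for the adjusted test. The adjusted variance is inflated by 1 + 1/(2n − 4) = 1 + 1/76 for estimating the slope. Effects are in pre-test SD. The last column is the power of the planned test at the effect for which the adjusted test has 80%.

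| k | rho | Variance saved | Detectable, planned | Detectable, adjusted | Power of planned test |
|---|---|---|---|---|---|
| 1 | 0.5 | 25% | 0.634 | 0.553 | 68.5% |
| 1 | 0.6 | 20% | 0.567 | 0.511 | 71.3% |
| 1 | 0.7 | 15% | 0.491 | 0.456 | 73.9% |
| 1 | 0.8 | 10% | 0.401 | 0.383 | 76.3% |
| 1.25 | 0.5 | 11% | 0.727 | 0.691 | 76.0% |
| 1.25 | 0.6 | 6% | 0.654 | 0.639 | 78.1% |
| 1.25 | 0.7 | 2% | 0.572 | 0.570 | 79.8% |
| 1.25 | 0.8 | 0% | 0.476 | 0.479 | 80.5% |
| 0.8 | 0.5 | 43% | 0.581 | 0.442 | 56.8% |
| 0.8 | 0.6 | 40% | 0.523 | 0.409 | 59.1% |
| 0.8 | 0.7 | 37% | 0.457 | 0.365 | 60.8% |
| 0.8 | 0.8 | 36% | 0.381 | 0.307 | 61.7% |

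At other sizes (rho 0.6, k = 1), the detectable effect goes from 0.658 to 0.594 with 30 per arm, and from 0.506 to 0.455 with 50 per arm.

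**Step 4: simulation.** 20,000 trials, 40 per arm, no dropout, planned versus adjusted:

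- rho 0.6, k = 1: type I error 5.1% vs 5.0%; power at 0.51 SD 71.6% vs 79.6%; 95% CI half-width 0.397 vs 0.358.
- rho 0.8, k = 1.25: type I error 5.0% vs 4.9%; power at 0.48 SD 80.6% vs 80.2%; half-width 0.333 vs 0.335.
- rho 0.6, k = 0.8: type I error 5.2% vs 5.0%; power at 0.41 SD 59.6% vs 80.3%; half-width 0.366 vs 0.286.

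Mean estimates were within 0.003 SD of the true effect for both methods.

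**Step 5: stratification factors.** Suppose age, gender and education explain R² = 5% to 20% of score level (assumed, k = 1). The within-stratum correlation is then rw = (rho − R²)/(1 − R²), and the residual variance goes from 1 − rho² to (1 − R²)(1 − rw²), which is 0.6% to 8% lower. Multiplying by (1 + 4/73)/(1 + 1/76), the cost of three more coefficients without balance, gives a net effect from a 3.5% loss to a 4.6% gain. Stratified blocking reduces that cost.

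**The case against.** The strongest reply is that a pre/post mixed ANOVA is a valid, prespecified analysis of this design, and that preferring another valid estimator corrects no error. The size is also uncertain: across the assumed range it runs from a 43% saving to a slight loss, and nothing in the documents favours k = 0.8, where the gain is largest. That stands as a limit on the size. It does not remove the point, because the large-sample saving is never negative and the worst case shown costs 0.003 SD.

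The table above uses the pre-test as the only covariate. With all four covariates, if the stratification factors explain nothing and are unbalanced, the detectable effect at k = 1.25 goes from 0.654 to 0.652 at rho 0.6, from 0.572 to 0.582 at rho 0.7, and from 0.476 to 0.489 at rho 0.8. This also stands. The reason to include those factors is that they define the randomisation strata, not a gain in precision.

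The sentence ruling out adjustments might mean that covariates were omitted on purpose. Neither it nor the exploratory list, which does name age, supplies the pre-test as a covariate. The sentence would need rewording.

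The assessments described for the MAP and test-retest arms cover knowledge and lifestyle, which overlap primary measures. The pre-allocation timing of the primary pre-test follows from Study Procedures and the Pre-/Post-test measures section together, and is worth confirming.

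Finally, the simulations had no dropout. If dropout depends on the pre-test score and differs by arm, the change-score comparison can be biased where the adjusted one need not be. That would strengthen the case for adjustment.

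**Conclusion.** The concern holds as a matter of efficiency. For the six primary measures the planned test leaves unused a pre-allocation score that the trial already collects. At k = 1 the variance saved is 25% to 10% for rho 0.5 to 0.8; it is smaller when the post-test SD is larger than the pre-test SD, larger when it is smaller, and nil when rho·k is near 1. The direction is well established; the size rests on assumed rho, k and completer numbers. The equivalence is exact for each pairwise comparison with complete data.

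The section names the intervention-control pair only for secondary outcomes. If all four groups enter one ANOVA for a primary outcome, the variance ratios hold but the degrees of freedom and power figures change.

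The conclusion is not extended to the secondary measures. Their heading describes them as embedded in the conditions, and the program descriptions include their own pre/post assessments, so their pre-test may follow allocation.

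**What to change.** For each primary outcome, prespecify a regression of the post-test score on group and pre-test score, with age, gender and education as fixed covariates because they are the stratification factors. Analyse the follow-up score the same way, separately, where both arms of the contrast have one. Report the adjusted group difference with its 95% CI. State what the sentence ruling out adjustments refers to, and confirm that every primary measure is taken at the pre-randomisation session.

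Two points need reconciling first:

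- **Secondary outcomes.** The Pre-/Post-test measures section gives all measures at every session, whereas the secondary-outcome heading and the program descriptions suggest assessment within the conditions. Use the model for these outcomes only if their pre-test precedes allocation.
- **MAP follow-up.** The test-retest group is described as having two assessments, but Study Procedures states: "Informed consent, pretest, posttest, and follow-up testing sessions will be completed online". Settle this before specifying any joint model of post-test and follow-up.

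For the primary outcomes the cost is SAP wording and about 4 of 78 degrees of freedom at 40 per arm (critical t from 1.991 to 1.993), more if education has several levels. In the least favourable case examined (rho 0.8, k = 1.25), the detectable effect is 0.476 as planned, 0.479 with the pre-test alone, and 0.489 with all four covariates if the stratification factors explain nothing and are unbalanced.

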1. Online Memory and Aging Program: consists of weekly modules, and will take approximately 10 hours to complete over eight consecutive weeks. The content of the program includes: (a) the provision of factual information (i.e., about memory, age-related memory changes, lifestyle factors affecting memory, and memory strategies); and (b) memory intervention (i.e., practice and application of several evidence-based memory strategies). The information is delivered in a variety of formats, including videos, animations, interactive games, discussion boards, and live chats. As in the in-person MAP, participants will complete homework assignments in a Participant Workbook that will be mailed to them at the onset of the intervention. The program includes pre/post

assessment of knowledge, memory and lifestyle behaviours, and personal goals for reducing impact of memory change.

2. Test-retest group: This group will complete two assessments of knowledge, memory and lifestyle behaviours, and personal goals for reducing impact of memory change. These assessments will include a mix of online questionnaires and a telephone interview. Our prior research has shown equal attainment of personal goals for memory and lifestyle change in the face-to-face Memory and Aging program and a test-retest condition. Participants in this group will be offered the opportunity to complete the online Memory and Aging Program after study completion.
3. Online Goal Management Training: consists of 9 weekly modules composed of videos, interactive applets, and assignments, which take about approximately 20 hours total to complete. The program presents factual information about automatic processing, teaches strategies to stop and control automatic processes while maintaining focus on the current task goals and sub-goals, provides assignments that raise awareness into participants' own automatic processing and cognitive control, and provides games that allow participants to practice and build on the strategies acquired throughout the program. The program includes pre/post online assessment of cognition.

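### The exploratory covariate rule can put engagement, a post-randomisation variable with no counterpart in the test-retest arm, into between-group models, and the plan does not clearly keep it out of the main tests

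*Combined protocol and SAP*

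**What the plan says.** The main analysis is a mixed-model ANOVA for each outcome, with group as the between-subjects factor. It compares pre-test with immediate post-test, and pre-test with follow-up. The hypothesis test is the interaction: "We expect significant interactions between group and pretest-posttest scores".

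The SAP then states: "No adjustments will be used for these primary and secondary" a priori analyses. It does not say whether this means adjustment for multiplicity or for covariates.

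A new paragraph follows: "We will also explore whether key variables including age, degree of engagement with the program, presence of subjective cognitive impairment, and computer familiarity covary". For any that track programme effects, the plan is: "and if so control for them by adding them as covariates in our statistical models". Engagement is not defined or given a scale for any arm. The trigger for adding a covariate and the form of the model are also not given.

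Study Procedures sets the timing: "Following completion of the pre-test assessment session, participants will be randomly assigned to one of four groups", and then "Participants will be informed of their group allocation by email and then begin the assigned program at their convenience". MAP "will take approximately 10 hours to complete over eight consecutive weeks". Its comparator, the test-retest group, has assessments only: "Participants in this group will be offered the opportunity to complete the online Memory and Aging Program after study completion".

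**The concern.** Three of the four listed variables (age, subjective cognitive impairment, computer familiarity) can be fixed at baseline. Engagement cannot. It is produced by the allocated programme and by the participant's response to it, so conditioning on it breaks the comparison that randomisation protects. In MAP versus test-retest it has no meaning on one side of the contrast.

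The rule is also data-driven: engagement enters when it appears related to the effect. That is when an engagement-adjusted contrast lies furthest from the effect of assignment. At stake is a between-group result described as controlled that understates or reverses a real programme effect. If the rule were applied to the main models, the group x time tests themselves would be affected.

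**Working it through.** **1. Timing.** The order is pre-test, randomisation, notice of allocation, programme. Engagement is therefore post-randomisation in every programme arm. Test-retest participants are offered MAP only after the study, so they have no engagement value while outcomes are collected.

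**2. Model form.** Each planned comparison uses two time points, so with complete data the group x time test equals a group test on change scores. In a check on 20 simulated complete two-time datasets, engagement as a main effect changed the group x time coefficient by at most 2.4e-15. With an engagement x time term, that coefficient equalled the engagement-adjusted change-score coefficient to within 1.4e-14. Harm therefore needs an engagement x time term or a change-score model. The SAP neither states nor excludes these.

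**3. What the adjusted contrast estimates.** Suppose engagement E is coded 0 throughout test-retest. Its slope b then comes from MAP alone, and

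adjusted group effect = (mean change in MAP − mean change in test-retest) − b × mean E in MAP.

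This is the MAP difference extrapolated to a MAP participant with zero engagement.

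**4. Inputs.** From the documents: 200 participants in four groups. Assumed: equal allocation without attrition (200/4 = 50 per arm); change SD 1; true effect 0.50 SD; E in MAP with mean/SD of 4/3, 6/2 or 7/1.5 modules; and a trait correlated 0.5 with E and 0.3 with change.

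**5. Always adjusting.** b = 0.5 × 0.3 × SD / SD² = 0.15/SD, so the expected adjusted effect is 0.50 − 0.15 × mean/SD:
- 4/3: 0.50 − 0.20 = 0.30
- 6/2: 0.50 − 0.45 = 0.05
- 7/1.5: 0.50 − 0.70 = −0.20

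The variance of the group effect is inflated by 1 + mean²/(2 × SD²), which gives 1.9, 5.5 and 11.9.

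**6. Adjusting only when triggered.** Here E is added only if its within-MAP correlation with change has p<0.05 (20,000 simulated trials per cell).

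| E mean/SD | Mean estimate when rule fires | Mean over all trials, true 0.50 | Rejection with no true effect |
|---|---|---|---|
| 4/3 | 0.04 | 0.42 | 11% |
| 6/2 | −0.54 | 0.32 | 16% |
| 7/1.5 | −1.12 | 0.22 | 18% |

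The rule fires in 17-18% of trials. The third column follows from the second: the shifts from 0.50 are 0.46, 1.04 and 1.62; multiplied by 0.175 they are 0.08, 0.18 and 0.28; subtracted from 0.50 they leave 0.42, 0.32 and 0.22. Rejection in favour of MAP is 0.57-0.58, against about 0.70 unadjusted. With no true effect, 9%, 14% and 16% of trials reject against MAP and about 2% in its favour.

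**7. Engagement unrelated to change.** The rule fires in about 5% of trials. Power is about 0.69 versus 0.70, and rejection with no true effect is 6-9%, split evenly by direction.

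**8. A different trigger.** If the screen pools both arms, it partly tests group itself. Rejection with no true effect is then not inflated (1.5-4%). At a true 0.50, however, rejection in favour of MAP falls to about 0.24, 0.06 and 0.02 with the shared trait, and to 0.50, 0.23 and 0.13 when engagement is unrelated to change. In the unrelated case the mean estimates are still about 0.42-0.45, so the loss there is mainly precision.

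**9. Goal Management Training (GMT) versus BrainHQ.** Both arms have a programme, so engagement exists in each. GMT's load is given as about 20 hours in total. BrainHQ's is given as about one hour weekly, with no programme length. The firm points are only that engagement is post-randomisation and has no defined common scale, so no size is claimed for this pair.

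**The case against.** The strongest reply is that these models are exploratory. The a priori analyses are closed off first, with a statement that no adjustments apply, and a new paragraph then announces further exploration. A reader might infer that the plan will adjust its primary tests for engagement. The documents do not support that. Even if the no-adjustment sentence concerns multiplicity alone, the opening of the next paragraph separately marks the covariate models as additional. What points the other way is that the models to receive covariates are not restricted to separate exploratory ones. Exposure of the main tests is therefore possible and no more.

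The second reply is that the harm depends on choices the SAP does not make. A main-effect covariate leaves group x time unchanged with complete two-time data. Coding engagement as 0 in test-retest is an assumption; if it were treated as missing, a complete-case model would drop that arm and leave no contrast to estimate. The trigger is assumed too, and changing it alone removes the inflation under no effect. All of this stands, and it is why the figures are illustrative. Against it, the stated trigger is covariation with the intervention effect, which suggests a term acting on change, though the text does not settle it.

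A reader might also infer that the rule manufactures efficacy. With a shared trait it does not: false rejection in favour of MAP stays at about 2%, and the error runs mainly against the programme.

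**Conclusion.** The concern holds in a limited form and should be fixed; confidence is moderate. The SAP contains a rule that can add a post-randomisation variable, absent from one arm of the MAP comparison, to between-group models. If it enters so that it acts on change, the group contrast is not the effect of assignment. On the most natural reading, the damage is confined to an exploratory result that could be reported as a controlled comparison. Because the type of adjustment ruled out is not stated and the target models are not restricted, the primary and secondary tests are not clearly protected.

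The size cannot be fixed from the documents. It ranges from negligible bias and power loss (within-MAP trigger, engagement unrelated to change) to severe loss of power (pooled trigger). The shared-trait results rest on zero coding in test-retest, the assumed correlations and trigger, 50 per arm, and a change-acting model form. The case for changing the text rests on timing and on the missing counterpart in test-retest, not on these figures.

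**What to change.** Remove engagement from the covariates of all between-group models, and limit covariates there to baseline variables. Examine engagement only as an exploratory association within each programme arm. Suggested wording:

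> The primary and secondary group x time tests will not be adjusted for engagement, and no between-group model will include it as a covariate. Engagement will be related to change within each programme arm only, as an exploratory analysis.

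Also state whether the no-adjustment sentence refers to multiplicity, covariates or both.

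The cost is two SAP sentences, with no new data and no change to the mixed-model ANOVA. The downside is that no engagement-controlled between-group result is reported. A separately labelled complier-average analysis of MAP versus test-retest, using randomisation as the instrument, is optional and not part of the required change.

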## **Method**

### **Study population**

200 healthy community-dwelling older adults will be recruited by newspaper and online advertisements (see Appendix).

Inclusion criteria:

[figure not shown]
- (a) Age 60+
- (b) Available to participate in all testing and intervention sessions and access to a computer
- (c) Computer familiarity
- (d) Cognitive complaint/concern/frustration

Exclusion criteria:

- (a) Health conditions with major effects on cognition, including a current or previous history of stroke, brain surgery, or diagnosed neurological disorder;
- (b) Dependence in instrumental activities of daily living
- (c) Cognitive impairment, defined as performance below cutoff for cognitive impairment on a standardized cognitive screening measure, the modified Telephone Interview for Cognitive Status (Welsh et al., 1993)
- (d) Affective impairment, defined as performance below cutoff for depression on standardized depression screen, the Geriatric Depression Scale (Yesavage et al., 1983)

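### The covariate rule answers apparent effect modification by age or computer familiarity with covariate adjustment chosen after seeing the effects; no interaction model or reporting is specified

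*Combined protocol and SAP*

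**What the plan says.** All of this is in the combined protocol and SAP. Under Statistical analyses, the model is given as follows: "Mixed-model ANOVAs will be used to examine pre-test and post-test scores on the outcome measures in the control and intervention groups". The programme effect is the group-by-time term: "We expect significant interactions between group and pretest-posttest scores". After the primary and secondary analyses comes one further, exploratory step. It names computer familiarity, age, engagement and subjective impairment, and asks of each whether it may "covary with the effects of the intervention, and if so control for them by adding them as covariates in our statistical models". No screening test, threshold or interaction term is named. The text does not say whether a covariate would enter as a main effect only or also with time.

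Two other places matter. Study Procedures says that "participants will be randomly assigned to one of four groups according to a blocked randomization scheme (stratified on age, gender, and education"), so age is a stratification factor. The same section expects dropout without giving a rate: "The estimate of the number of participants reflects the expectation of attrition due to the length of the study".

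This point concerns age and computer familiarity as baseline variables. Degree of engagement arises after randomisation and raises a different problem. Presence of subjective impairment overlaps with inclusion criterion (d). Neither is treated here.

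**The concern.** A variable that covaries with the effect of the intervention is an effect modifier. Describing it requires a term that lets the group-by-time effect differ across its values. The plan instead adds it as a covariate, which assumes the same effect at every value, the very assumption the screen has just called into question. In a randomised comparison a baseline modifier is not a confounder, apart from chance imbalance, so there is no bias that calls for this control.

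The selection criterion is also the wrong one. Covariates earn a place in the main model by predicting the outcome, or by being stratification factors, and they are chosen before the data are seen. Here an apparent interaction decides, after a look at the effects.

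Two things are at stake. One is a practical question for an online programme for people aged 60 and over: does benefit depend on age or computer familiarity? The other is whether every outcome is analysed with the same model.

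**Working it through.** The documents give no alpha, effect size, standard deviation or power, so there is no stated figure to reproduce.

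**Inputs from the documents.** 200 participants (Study population), four groups (Study Procedures), six primary measures (Primary Outcome Measures), and two contrasts, pre-test to immediate post-test and pre-test to follow-up (Statistical analyses). **Assumed.** Equal allocation, so 200/4 = 50 per arm; screening at two-sided 5%; other assumptions as stated at each step.

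**1. What each form of covariate does.** Let g be group, t be time (0 or 1) and x a baseline variable. With complete data the pre-post change has expectation:

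- no covariate: b2 + b3·g
- x as a main effect: b2 + b3·g (x is the same at both times and cancels)
- x and x·t: b2 + b3·g + b5·x
- g·t·x model: b2 + b3·g + b5·x + b6·g·x

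Only the last lets the effect vary, as b3 + b6·x.

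**2. Numerical check.** Random-intercept models were fitted to simulated data: 50 per arm, pre-post correlation 0.6, true group x time effect 0.5, true modification 0.3 per SD of x. The table shows one data set with complete data and a separate one with 20% post-test dropout, so compare within columns only.

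| Model | group x time, complete (SE) | group x time, 20% dropout |
|---|---|---|
| no covariate | 0.5587 (0.1664) | 0.8017 |
| + x | 0.5587 (0.1664) | 0.7913 |
| + x and x·t | 0.5844 (0.1566) | 0.7514 |
| three-way | 0.6170 (0.1536) | 0.7406 |

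Over 2,000 complete-data replicates, adding x·t moved the estimate by 0.040 on average (95th percentile 0.108), while its mean stayed at 0.50. The three-way model recovered the modification: mean 0.301 against a true 0.30.

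**3. How often the screen fires by chance.** With two variables and no true modification, the rate per outcome-contrast is 1 − 0.95² = 0.0975, about 10%. Per programme there are 2 × 6 × 2 = 24 screens, so P(at least one) = 1 − 0.95²⁴ = 0.708 if they are independent. With a common correlation among the 12 screens for each variable (assumed), this becomes about 64%, 54% and 41% at correlations of 0.3, 0.5 and 0.7.

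**4. Type I error.** Simulating the rule under the null (20,000 runs, 50 per arm) gave a trigger rate of about 0.10 and a type I error of 0.050 to 0.051.

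**5. Precision.** Assume a standardised effect of 0.5 on change and a covariate that explains 9% of change variance. By the normal approximation, power without the covariate is Φ(0.5/√(2/50) − 1.96) = Φ(0.54) = 0.705. With x and x·t always included, the SD falls to √0.91 and power is Φ(2.5/√0.91 − 1.96) = Φ(0.66) = 0.746. Simulation gave 69.7% unadjusted, 69.9% under the rule and 73.2% always adjusted.

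**6. Power for modification itself.** With change SD 1, the SE of b6 per SD of x is about 2/√(2n), which is 0.20 at n = 50. For 0.3 per SD, power is Φ(1.5 − 1.96) = 32%; for 0.5 per SD, Φ(2.5 − 1.96) = 71%. At 40 per arm these are 27% and 61%.

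**The case against.** The strongest reply is that this is one exploratory sentence placed after the a priori analyses. The SAP also says "No adjustments will be used for these primary and secondary" analyses. That most naturally refers to multiplicity. If it covers covariates too, the main tests stay unadjusted and the covariate models are supplementary. This is a fair reading, but the text adds covariates to the statistical models without restricting which ones, so the ambiguity remains and should be closed.

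Four stronger readings are tempting, and the documents do not support them.

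- *Adding the covariate does nothing to the group-by-time estimate.* This is exact only for a time-constant main effect with complete data. The plan does not fix that form and it expects attrition. It also cannot be combined with a claim of lost precision, because the gain in step 5 requires a covariate-by-time term.
- *The plan never estimates who benefits.* Exploring whether a variable covaries with the effect may itself produce such an estimate. What is missing is a specified model and form of reporting.
- *Most programmes will have a model altered by chance.* The 71% figure needs an assumed threshold and independence. The contrasts share a pre-test and the same people complete all the measures, so independence is implausible.
- *Age needs no place in any model.* As a stratification factor it has a sound reason to be in the main model, whatever the screen shows.

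Computer familiarity is also an inclusion criterion, so its range may be narrow and any modification by it hard to detect.

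**Conclusion.** The point holds and is minor. The SAP meets apparent effect modification with additive adjustment, which cannot describe it, and lets a look at the effects decide the covariates. The models can then differ between outcomes by chance, in about 10% of outcome-contrasts for two baseline variables under an assumed 5% screen.

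The main test is not shown to be at risk. Type I error is not materially inflated, and the estimate moves only slightly through chance imbalance or dropout. The forgone power is about 3 to 4 percentage points, and only if a covariate explains 9% of change variance and the effect is 0.5 SD. Neither figure is in the documents. Power to detect modification is low for moderate values, which favours reporting estimates with intervals over a rule triggered by significance.

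**What to change.** Replace the covariate sentence, for these two variables, with:

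> For age and computer familiarity at baseline we will fit the group x time x variable interaction for each outcome and report the group x time effect at low and high values (fixed in advance) with 95% CIs, as exploratory and with low power acknowledged. The main group x time analysis will not be changed by these results. Its covariates are fixed in advance as the stratification factors (age, gender, education), each entered with its time interaction.

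The time interactions are needed because a main effect alone cancels from the change when data are complete. The SAP should also say what the statement about no adjustments refers to.

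Cost: revised SAP wording, one extra exploratory model per variable and outcome, and a few degrees of freedom in the main model. No new data are needed, provided screening or the pre-test records computer familiarity on a usable scale; the listed outcome measures do not name one.
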